## 12. Quality control and quality assurance

## **12.1.** Site Set-up and Initiation

All participating Principal Investigators will be asked to sign the necessary agreements and supply a current curriculum vitae (CV) to the NCTU. All members of the site research team will also be required to be entered onto a site delegation log signed by the individual staff member and the Principal

Trial	TB-DILI Trial	Protocol	1.2	date:	02-Aug-2022	Page 44 of 58
name:		version:				

Investigator. Prior to commencing recruitment all sites will undergo a process of initiation and will have completed appropriate GCP training. Key members of the site research team will be required to attend either a meeting or a teleconference covering aspects of the trial design, protocol procedures, Adverse Event reporting, collection and reporting of data and record keeping. Sites will be provided with an Investigator Site File containing essential documentation, instructions, and other documentation required for the conduct of the trial. The NCTU must be informed immediately of any change in the site research team.

# 12.2. Monitoring

# 12.2.1. On-site Monitoring

Monitoring will be carried out as required following a risk assessment and as documented in the monitoring plan. Any on site monitoring activities will be reported to the Sponsor and any issues noted will be followed up to resolution. On-site monitoring visits may be triggered, for example by poor CRF return, poor data quality, lower than expected SAE reporting rates, excessive number of participant withdrawals or deviations. If a monitoring visit is required, the NCTU will contact the site to arrange a date for the proposed visit and will provide the site with written confirmation. Investigators will allow the TB-DILI trial staff access to source documents as requested.

# 12.2.2. Central Monitoring

The NCTU will be in regular contact with the site research team to check on progress and address any queries that they may have. The trial team will check incoming eCRF data against the criteria for monitoring outlines in the monitoring plan. Sites will be requested to send in copies of signed ICFs and other documentation for internal review a predefined number of participants. All details of proposed central monitoring will be detailed in the monitoring plan.

# 12.3. Audit and Inspection

The Principal Investigator will permit trial-related monitoring, quality checks, audits, ethical reviews, and regulatory inspection(s) at their site, providing direct access to source data/documents. The Principal Investigator will comply with these visits and any required follow up. Sites are also requested to notify the Trials Office of any MHRA inspections. The trial will be subject to internal audit (system and trial level) on a risk basis.

The Trial Master File and evidence of audits will be made available upon request for regulatory inspections.

# 12.4. Notification of Serious Breaches

In accordance with Regulation 29A of the Medicines for Human Use (Clinical Trials) Regulations 2004 (and subsequent amendments) the Sponsor of the trial is responsible for the oversight of notification to the licensing authority of any serious breach of the conditions and principles of GCP in connection with that trial or the protocol relating to that trial. It is the responsibility of NCTU to notify the licensing authority, in writing within 7 days of becoming aware of a breach and confirm this has been communicated with the Sponsor.

For the purposes of this regulation, a "serious breach" is a breach which is likely to effect to a significant degree the safety or physical or mental integrity of the subjects of the trial; or the scientific value of the trial. Sites are therefore requested to notify the NCTU of any suspected trial-related serious breach of GCP and/or the trial protocol. Where the NCTU is investigating whether or not a

Trial	TB-DILI Trial	Protocol	1.2	date:	02-Aug-2022	Page 45 of 58
name:		version:				

serious breach has occurred sites are also requested to cooperate in providing sufficient information to report the breach to the MHRA and REC where required and in undertaking any corrective and/or preventive action.

Sites may be suspended from further recruitment in the event of serious and persistent noncompliance with the protocol and/or GCP, and/or poor recruitment. Any major problems identified during monitoring may be reported to the trial oversight committees (Trial Management Group, Trial Steering Committee, DMC), the REC and the relevant regulatory bodies. This includes reporting serious breaches of GCP and/or the trial protocol to the REC and MHRA.

# 13. End of Trial Definition

The end of trial will be the date of final database lock. This will allow sufficient time for the completion of protocol procedures, data collection and data input. The NCTU will notify the MHRA and REC that the trial has ended within 90 days of the end of trial. Where the trial has terminated early, the NCTU will inform the MHRA and REC within 15 days of the end of trial and provide them with a summary of the clinical trial report within 12 months of the end of trial.

# 14. Statistical Considerations

# 14.1.1. Power Calculations / sample size calculation

Assuming 10% of participants in the 4-drug group and 1.5% in the 3-drug group experience DILI recurrence, then a recruited sample size of 175 per arm would provide 90% power to detect this difference (with a two-sided type-I error of 5%), allowing for up to 10% non-collection of primary outcome data due to loss-to-follow-up and mortality giving 157 per arm for analysis2,3. This calculation is based on a two-sided Z-Test with pooled variance.

Table 5 describes the smallest detectable absolute difference in proportions for a trial randomising 175 participants per group with varying rates of loss to follow-up, with a power of either 80% or 90% (and a two-sided type-I error of 5%), and assuming various rates of DILI recurrence.

recurrence.							
Loss to	Effective		Perce	ntage of DILI	recurrence ir	n 4-drug grou	ıp (%)
follow-up	sample size per group	Power (%)	10	15	20	25	30
10%	157	80	7.6	9.6	11.1	12.3	13.3
1076		90	8.5	10.7	12.5	14.0	15.2
5%	166	80	7.4	9.3	10.8	12.0	13.0
J70	100	90	8.3	10.5	12.2	13.6	14.8
None	175	80	7.3	9.1	10.6	11.7	12.7
None	1/3	90	8.1	10.3	12.0	13.3	14.5

Table 5: Smallest detectable absolute reduction in risk for a trial randomising 175 participants per group with varying rates of loss to follow-up (LTFU) and assuming various proportions of DILI recurrence.

Trial	TB-DILI Trial	Protocol	1.2	date:	02-Aug-2022	Page 46 of 58
name:		version:				

# 14.2. Analysis of Outcome Measures

# 14.2.1. Planned Interim Analysis

No formal interim analyses are planned. However, an internal pilot has been built into the trial to allow a feasibility assessment which will examine recruitment and retention. This will be continually monitored, and a formal review will take place 18 months after the first participant has been randomised. Recruitment will be measured against the overall recruitment target at 18 months. To assess retention in the maximum number of participants at 18 months, retention is defined as the proportion of participants for whom the primary outcome is evaluable a) at 12 months for participants recruited within the first six months, b) at end of treatment for subsequent recruits.

	Black (stop the study)	Red (proceed with recovery plan)	Amber (proceed with changes)	Green (proceed)
% Threshold				
Trial recruitment	<50%	50 – 79%	80- 99%	> 100%
Recruitment rate (site/month)	<0.12	≥0.12 - ≤ 0.18	> 0.18 - <0.23	> 0.23
Retention (primary outcome obtained)	<50%	50-79%	80 – 99%	> 100%
Adherence*	<50%	50-74%	75-89%	> 90%

Table 6: Internal pilot progression criteria.

\*Adherence defined in section 7.5.2.

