## 16.5. Data Monitoring Committee

Reports will be supplied in confidence to an independent DMC, which will be asked to give advice on whether the accumulated data from the trial, together with the results from other relevant research, justifies the continuing recruitment of further participants. The DMC will operate in accordance with a trial specific charter based upon the template created by the Damocles Group.

During the recruitment phase of the trial, the DMC is scheduled to meet 6 months and 18 months after the recruitment of the first participant and annually thereafter.

Additional meetings may be called if recruitment is much faster than anticipated and the DMC may, at their discretion, request to meet more frequently or continue to meet following completion of recruitment. An emergency meeting may also be convened if a safety issue is identified. The DMC will report directly to the TSC who will convey the findings of the DMC as appropriate (e.g. MHRA, funder, and/or Sponsor).

At the first DMC meeting, the committee will be presented with the data required to assess the stopgo criteria for the internal pilot phase of the trial (see section 14.2.1). The DMC and TSC will review the data against the stop-go criteria and advise whether the trial should continue, outlining any concerns/modifications required for continuation (if applicable).

Trial	TB-DILI Trial	Protocol	1.2	date:	02-Aug-2022	Page 49 of 58
name:		version:				

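### The internal-pilot criteria contradict the protocol's own plan: retention is green only at 100% although 10% loss is allowed for, and the stop-go review is placed at both month 6 and month 18

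*Protocol*

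**What the plan says.** Section 14.2.1 plans no formal interim analysis but has an internal pilot, for which "a formal review will take place 18 months after the first participant has been randomised". Table 6 scores the row "Retention (primary outcome obtained" as black (stop) below 50%, red (recovery plan) at 50 to 79%, amber (changes) at 80 to 99% and green (proceed) at 100% or more. The adherence row of the same table is green from 90%.

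The text above the table says "retention is defined as the proportion of participants for whom the primary outcome is evaluable", taken at 12 months for recruits of the first six months and at end of treatment (EoT) for later ones. It adds: "Recruitment will be measured against the overall recruitment target at 18 months".

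Section 14.1.1 sets the recruited size at 175 per arm, "allowing for up to 10% non-collection of primary outcome data", which leaves 157 per arm.

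Section 16.5 says "the DMC is scheduled to meet 6 months and 18 months after the recruitment of the first participant" and then annually. It continues: "At the first DMC meeting, the committee will be presented with the data required to assess" the stop-go criteria, with a cross-reference to section 14.2.1, after which the DMC and TSC advise on continuation.

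**The concern.** Progression criteria should separate a trial that is performing as designed from one that is not. Here the retention target for an unqualified go-ahead is stricter than the retention on which the power calculation rests. A single uncollected outcome takes the trial out of green, and one amber band covers everything from near-perfect follow-up down to a loss twice the planned allowance.

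The timing conflict is a separate defect. The committee is handed the stop-go data at a meeting a year before the review that section 14.2.1 describes, when the retention measure has almost nothing to act on. At stake are an unwarranted instruction to change the trial and uncertainty about when the committees are to decide. The primary analysis, type I error and planned power are not touched.

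**Working it through.** **1. The plan's own sample size.** Inputs from section 14.1.1: "Assuming 10% of participants in the 4-drug group and 1.5% in the 3-drug group experience DILI recurrence", 90% power, two-sided 5%, Z-test with pooled variance.

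n = [1.960·√(2·p̄·(1−p̄)) + 1.2816·√(p1(1−p1) + p2(1−p2))]² / (p1−p2)², with p̄ = (0.10 + 0.015)/2 = 0.0575.

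n = [1.960·√0.10839 + 1.2816·√0.10478]² / 0.085² = (0.6453 + 0.4148)² / 0.007225 = 155.5, so 156 per arm. Dividing by 0.90 gives 174, and 175 × 0.90 = 157.5. Power at 157 per arm is 0.903. The stated 175, 157 and 90% are reproduced, so 90% retention is what the design needs. At 80% retention (140 per arm) power is about 0.87.

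**2. How many are assessable at month 18.** The protocol gives 350 participants over 48 months. Assuming even accrual, 350 × 18/48 = 131 are recruited by month 18. All recruits of months 0 to 6 have then reached 12 months. Later recruits have reached EoT if randomised early enough. With EoT at 24 weeks (5.52 months) in the control arm and 36 weeks (8.28 months) in the intervention arm:

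- control: (18 − 5.52)/18 = 0.693
- intervention: (18 − 8.28)/18 = 0.540
- mean 0.617, and 0.617 × 131.25 = 81 people.

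**3. Chance of green at 100%.** If true retention is r and n people are assessable, P(green) = rⁿ.

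| True retention | n = 44 | n = 81 | n = 131 |
|---|---|---|---|
| 90% | 0.0097 | 0.0002 | 0.000001 |
| 95% | 0.105 | 0.016 | 0.001 |
| 98% | 0.41 | 0.19 | 0.07 |
| 99% | 0.64 | 0.44 | 0.27 |

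Here 44 is the number recruited in the first six months (350 × 6/48), and 131 is everyone recruited by month 18.

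**4. Colour at the planned 90%.** With n = 81, amber means 65 to 80 outcomes obtained. The exact binomial gives green 0.0002, amber 0.997, red 0.002 and black about 0.

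**5. What exists at month 6.** Nobody has been followed for 12 months. With a 24-week control course, the share of control recruits past EoT is (6 − 5.52)/6 = 0.08. No intervention recruit has finished. The overall share is 0.08/2 = 0.04, about 2 of 44 people. With a full 6-month course it is zero.

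**6. If all recruits were the denominator at month 18.** EoT was varied over 24/32 weeks, 24/36 weeks, 25/37 weeks and 6/9 months. This covers both intervention-arm timings in the protocol: Figure 2 puts the EoT contact at week 33 and section 9.1.4 at week 37, which must be reconciled. Between 58% and 64% of recruits could have reached their time point. After 10% loss that is 52 to 58%, which scores red.

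**7. The proposed threshold.** With green at 90% or more and n = 81, a trial at exactly 90% true retention is green with probability about 0.58. With green at 85% or more it is about 0.94.

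**The case against.** The strongest defence is that these are advisory feasibility criteria, applied by committees that can see why a figure falls short. The 10% is also a ceiling. Section 9.4 recovers outcomes from medical records or NHS Digital. Section 14.2.2 counts treatment completers without recurrence as non-events and expects very little missing data. So true retention may well exceed 90%. That is fair, and it limits the harm, but it does not rescue a 100% threshold: very little is not none, and at 99% retention green is still less likely than not with 81 assessable.

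On timing, section 16.5 points back to section 14.2.1 and an 18-month DMC meeting is already scheduled, so month 18 is probably intended. The text nevertheless names the first meeting.

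A reader might infer more: that the rules would stop a trial that is on plan. The documents do not support this.

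- The 100% rule alone gives amber.
- Counting recruits who cannot yet have an outcome is one reading of an unclear definition. The stated aim of assessing as many participants as possible also fits a denominator of those who have reached their time point. Even on the first reading, even accrual at month 18 gives red. Black there needs slower early accrual, which the protocol does not describe.
- Scoring recruitment as 131/350 = 37.5%, below the stop line, takes the target to be all 350. Green would then mean completing a 48-month recruitment by month 18, which cannot be meant.
- The green site rate of 0.23 per month is not itself an error. It would give 0.23 × 40 × 48 = 442 participants only if all 40 sites were open throughout. It fits 350 with 350/0.23 = 1,522 site-months, for example with sites opening steadily over about 20 months.
- The 5.3% deaths and 4.2% losses in section 1.1 are national background figures, not trial assumptions.

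**Conclusion.** Two defects stand on the text. The green threshold for retention contradicts the sample size allowance: at 90% retention the trial is amber with probability about 0.997, so the row cannot distinguish planned follow-up from a shortfall. This figure rests on even accrual and about 81 assessable participants, but the conclusion does not depend on them: at 90% retention, green has probability below 0.01 for any number from 44 to 131. The timing of the stop-go assessment is contradictory, and at month 6 the retention criterion cannot sensibly be applied.

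Three lesser points need clarifying: who is in the retention denominator, what number recruitment is compared with at month 18, and the site rate of 0.18, which as printed falls in both red and amber. The last is a single boundary value, though the planned average with all sites open throughout, 350/(40 × 48) = 0.182, lies close to it.

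The expected consequence is an unwarranted amber and doubt about when to decide, not a mistaken stop. This should be fixed, but it does not threaten the trial's main result.

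**What to change.** - **Table 6, retention:** green at 90% or more, amber 80 to 89%, red 50 to 79%, black below 50%. This matches the 10% allowance and the adherence row. The sponsor should accept knowingly that a trial at exactly 90% true retention would still miss green about 42% of the time (1 − 0.58) by chance.
- **Section 16.5:** have the stop-go criteria assessed at the 18-month DMC meeting. Section 16.4 already schedules a TSC meeting at 18 months too.
- **Section 14.2.1, retention:** state that the denominator is participants whose 12-month date (recruits of the first six months) or planned EoT date (later recruits) has passed.
- **Section 14.2.1, recruitment:** state the number due by month 18 from the site-opening plan, and that recruitment is scored against it and not against 350.
- **Table 6, site rate:** assign 0.18 to one band only.

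The cost is an edit to Table 6 and a few sentences in two sections. No new data, meetings or participants are needed.

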# 14.2.2. Planned Final Analyses

The analysis and reporting of the trial will be in accordance with CONSORT guidelines, with the primary comparative analyses being conducted according to randomised allocation with due emphasis on confidence intervals for between-arm comparisons. A full statistical analysis plan will be developed prior to unblinding the trial statistician.

Descriptive statistics of demographic and clinical measures will be used to assess balance between the randomised arms at baseline, but no formal statistical comparisons will be made. Continuous variables will be summarised in terms of the mean, standard deviation, median, lower and upper quartiles, minimum, maximum and number of observations. Categorical variables will be summarised in terms of frequency counts and percentages.

The primary comparative analysis will employ generalised linear mixed effects regression modelling to compare the proportion with a DILI recurrence at 12 months in each group, adjusting for minimisation variables. The comparison will be presented as both an absolute (risk difference) and relative (risk ratio) effect, along with 95% confidence intervals. Secondary outcomes will be analysed using appropriate mixed effects regression models dependent on data type (binary, continuous, survival etc.), adjusting for minimisation variables.

The primary approach to between-group comparative analyses will be by intention-to-treat, that is including all participants according to randomised allocation regardless of adherence. Participants

Trial	TB-DILI Trial	Protocol	1.2	date:	02-Aug-2022	Page 47 of 58
name:		version:				

who complete treatment without DILI recurrence will be assumed to not meet the primary outcome (i.e., no recurrence of DILI), unless there is evidence to the contrary. All available evidence indicates the risk of ATT-DILI following cessation of drugs can be assumed as zero (no published reports known). Using this approach, we expect there to be very little missing primary outcome data but will use multiple imputation if required so that all randomised participants may be included in the primary analysis.

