# 1 Background and Rationale

## 1.1. Background

In 2018, 4,655 people were diagnosed with tuberculosis (TB) in the UK, equivalent to a rate of TB of 8.3 per 100,000 population. This was the lowest recorded rate of TB in the UK for the last 10 years. People born outside the UK accounted for 72% of notifications in 2018. The proportion of people with drug-sensitive TB who completed treatment by 12 months was 84.7% in 2017; in addition, 5.3% died and 4.2% were lost to follow up. Only 2.7% of people with TB were coinfected with HIV in 2018; most (81.7%) were born outside the UK. Early data from 2019 suggests that the rate of TB may be higher in 2019 compared to 2018.

The standard treatment of drug-sensitive TB involves a 4-drug combination of anti-TB therapy (ATT) for 2 months (intensive phase of treatment), followed by a 2-drug combination for 4 months (continuation phase of treatment), making a total treatment duration of 6 months. Cure rates are around 97%.9

Drug-induced liver injury (DILI) is the commonest serious adverse effect of ATT. DILI may result from direct toxicity of the primary compound or an immunological response to one or more of the drugs. Unpredictable or idiosyncratic reactions which develop acutely account for most types of DILI. These reactions are unpredictable based on the pharmacological action of the drug, independent of drug dose and are relatively unusual for each drug.

Among those who develop DILI on ATT, 16% develop jaundice and 5.3% acute liver failure; the latter is the most severe outcome of DILI, of which 22% can be fatal. Most patients with DILI who report symptoms experience nausea, vomiting, anorexia and lethargy. Early detection of DILI with cessation of the inciting drug(s) serves to limit the severity of DILI and its consequences. Not all asymptomatic increases in liver enzymes while on ATT constitute DILI episodes. Some of the increase in liver enzymes are self-limiting or are attenuated through a process called hepatic adaptation (please see later). However, very high levels of liver enzymes (>5x upper limit of normal) in the absence of symptoms are thought to represent early DILI episodes that, if left untreated (ie. continued exposure to the inciting drug(s)), would progress to symptomatic DILI.

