## 6.2. Randomisation

Eligible patients will be individually randomised on a 1:1 ratio to one of the treatment groups using an online randomisation system developed and maintained by the NCTU. Access to the system will be granted by the NCTU in accordance with the roles delegated by the Principal Investigator on the Site Delegation Log.

Treatment will be assigned using a minimisation algorithm balancing on the following factors:

- Recruitment site
- Participant's age ( $\leq$  35 and >35 years)
- Participant's worst severity of DILI up to randomisation (mild and moderate/severe)

The randomisation algorithm will include a probabilistic element to allocation making prediction of the allocated group virtually impossible.

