## 9.1.2. Baseline Assessments

Prior to randomisation, all relevant clinical data will be submitted to the DILI-adjudication panel. The panel will review the clinical information to determine that the patient is experiencing/has experienced a DILI event related to treatment of TB with standard 4-drug ATT. The patient will also be asked to complete the EQ-5D-5L, a quality-of-life questionnaire.

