# 15. Health Economics

Quality of Life will be measured using an online questionnaire to collect EQ-5D-5L data, with patients prompted by email / text message, and/or telephone. Patients who cannot use the online system will provide information by telephone

Quality of Life will be measured at 5 junctures for all participants: i) during initial DILI, ii) after DILI recovery prior to start of ATT, iii) 2 weeks after starting ATT, iv) one week after the end of ATT and v) at 12 months post-randomisation (the primary outcome). Participants with a DILI recurrence will have 2 additional measurements, vi) during DILI recurrence and vii) after recovery from DILI recurrence when on ATT. This is to enable assessment of the QoL impact of initial DILI (against a background of QoL detriment due to active TB and ATT, comparing i and ii), recurrent DILI (comparing vi and vii), TB disease under treatment (comparing ii and iii), and ATT (comparing iii and iv, and iii and v). The two arms of the trial will be compared using measurements i and v.

To enable healthcare resource costs to be calculated based on staff costs (determined by time and grade), drugs costs (from the British National Formulary), and costs of tests (NHS tariffs), we will record information on health services used by participants relevant to TB care during treatment and follow-up. This will include clinic visits, home visits, additional drugs used, and additional clinical resources required to manage recovery from DILI (e.g. ICU care). Relevance of services used to TB care will be determined by the attending TB team.

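### The protocol does not say how the pre-randomisation EQ-5D-5L reading enters the arm comparison; it should be a covariate for the 12-month reading, not the start of a change score

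*Protocol*

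**What the plan says.** Protocol section 14.2.2 gives one general sentence for the secondary outcomes: "Secondary outcomes will be analysed using appropriate mixed effects regression models dependent on data type (binary, continuous, survival etc.), adjusting for minimisation variables". Section 6.2 lists the minimisation factors: recruitment site, age split at 35 years, and "Participant's worst severity of DILI up to randomisation (mild and moderate/severe"). EQ-5D-5L is not among them.

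Section 15 deals with EQ-5D-5L itself. It sets five readings for every participant, beginning "i) during initial DILI, ii) after DILI recovery prior to start of ATT" and ending "v) at 12 months post-randomisation (the primary outcome"). It then says: "The two arms of the trial will be compared using measurements i and v".

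Reading i is a true baseline. Section 9.1.2 places it among the assessments made before randomisation: "The patient will also be asked to complete the EQ-5D-5L, a quality-of-life questionnaire".

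**The concern.** Two sections each prescribe part of the same analysis and do not meet. Section 14.2.2 names an adjustment set that does not contain reading i. Section 15 brings reading i into the arm comparison but gives it no role in a model. An analyst who follows both could reasonably do either of two things:

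- Analyse the change from i to v, adjusted for site, age group and severity.
- Analyse v, adjusted for site, age group and severity, with i only tabulated.

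The more precise choice, v adjusted for i as well, is the one the text does not mention.

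The choice matters more than usual here because of when reading i is taken. It is recorded in the acute phase of liver injury. Reading v comes a year after randomisation, when treatment is normally over. The correlation could well be modest, and a change score does worst when the correlation is low. At stake is the precision of the only between-arm quality-of-life comparison that section 15 specifies.

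**Working it through.** **The plan's own figure.** The only sample size in the protocol (section 14.1.1) is for DILI recurrence: 10% against 1.5%, two-sided 5%, 90% power, pooled Z-test. With mean proportion 0.0575:

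n = [1.960·√(2·0.0575·0.9425) + 1.2816·√(0.10·0.90 + 0.015·0.985)]² / 0.085² = (0.645 + 0.415)² / 0.007225 ≈ 155.5, so 156 per arm.

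156/0.9 gives 174 recruited, and power at 157 per arm is 90.3%. The stated 157 and 175 are therefore reproduced. They say nothing about EQ-5D-5L, for which no standard deviation (SD), correlation or power is given. I use 157 per arm below only as a plausible number analysed.

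**Inputs for EQ-5D-5L.** r is the correlation between readings i and v that remains after the minimisation variables. It is not in the documents, so I assume 0.2 to 0.7. The SDs of i and v are assumed equal.

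**Variance of the arm difference, relative to v alone (= 1):**

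- v with i as covariate: 1 − r²
- change from i to v: 2(1 − r)

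The smallest difference detectable with 90% power, in SDs of v, is (1.960 + 1.2816)·√(2·V/157), where V is the relative variance. For v alone it is 0.366 SD. The equivalent number is 157·(1 − r²)/[2(1 − r)] = 157·(1 + r)/2. This is the number per arm that, with the covariate analysis, would match a change score in 157.

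| r (assumed) | V, i as covariate | V, change score | Detectable, covariate | Detectable, change | Change score equivalent to |
|---|---|---|---|---|---|
| 0.2 | 0.96 | 1.60 | 0.358 SD | 0.463 SD | 94 of 157 |
| 0.3 | 0.91 | 1.40 | 0.349 SD | 0.433 SD | 102 of 157 |
| 0.5 | 0.75 | 1.00 | 0.317 SD | 0.366 SD | 118 of 157 |
| 0.7 | 0.51 | 0.60 | 0.261 SD | 0.283 SD | 133 of 157 |

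**Reading the table.** Below r = 0.5 a change score is less precise than ignoring reading i altogether. Above 0.5 it beats v alone but still falls short of the covariate analysis. Leaving i out costs 4% of the variance at r = 0.2 and 49% at r = 0.7.

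**Does the ranking depend on equal SDs?** No. If k is the SD of i divided by the SD of v, the change score has relative variance 1 + k² − 2rk, while the covariate analysis stays at 1 − r². The difference is (k − r)², which is never negative. With k = 1 it is (1 − r)², or 0.64, 0.49, 0.25 and 0.09, matching the gaps in the table. Only the sizes depend on the assumption.

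**The case against.** The strongest defence is that the sentence in section 14.2.2 is generic, calls for appropriate models, and sits beside a commitment to write a full statistical analysis plan. Outcome-specific covariates are ordinary content for that plan, which is not available here. This has force and is the main reason why the point is minor. It does not remove the point, because the protocol is not silent: it names an adjustment set in one place and a pair of readings in another, and the two leave the role of reading i open.

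Three stronger readings are tempting, and the documents do not support them.

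- *A reader might infer that covariates are restricted to the minimisation variables, so that reading i is thrown away.* The sentence does not say that nothing else may be added, and section 15 expressly brings reading i into the comparison.
- *A reader might infer that a change score is prescribed.* The preceding sentence in section 15 pairs readings to describe the impact of liver injury, disease and treatment, which leans that way. The sentence on the arms is worded differently, though, and would also fit baseline adjustment. The change score is a permitted reading, not a stated one.
- *A reader might infer that deaths fall out of the comparison, against the rule of "including all participants according to randomised allocation regardless of adherence".* A participant who dies cannot give reading v. The background section reports for national drug-sensitive TB that "in addition, 5.3% died and 4.2% were lost to follow up", and 5.3% of 175 is about 9 per arm. But the protocol prescribes no survivors-only analysis, the quoted rule concerns adherence, and 12-month mortality is a secondary outcome in its own right. The national rate need not apply to this population. With equal mortality and equal survivor means, scoring deaths as 0 would not move the difference at all. How deaths count, and whether 0 is a sensible value in a single 12-month comparison, belongs in the analysis plan or the health economics plan.

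It is also fair to say that if r is low, the gain over v alone is small (4% at 0.2, 9% at 0.3). The larger losses arise only if the change score is the one adopted.

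**Conclusion.** The point holds as a precision issue in a secondary outcome. As written, sections 14.2.2 and 15 permit two analyses of EQ-5D-5L, and neither is more precise than v adjusted for reading i. Against that analysis, a change score has 1.18 times the variance at r = 0.7 (0.60/0.51) and 1.67 times at r = 0.2 (1.60/0.96). Leaving i out has 1.04 times at r = 0.2 (1/0.96) and 1.96 times at r = 0.7 (1/0.51).

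The sizes rest on an assumed range for r and on equal SDs. The ranking rests on neither. Because severity is already in the model and may absorb part of what reading i carries, the remaining correlation could lie towards the lower end of the range.

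Randomisation protects all three analyses from bias in expectation, so validity is not in question. The primary outcome is untouched. The impact is minor, and the improvement is essentially free.

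**What to change.** Put one consistent statement in section 14.2.2 and section 15 (and carry it into the analysis plan): the quality-of-life outcome for the arm comparison is EQ-5D-5L at 12 months (reading v), modelled with reading i as a covariate in addition to site, age group and DILI severity. State that change from reading i will not be the analysed outcome.

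Reading i is the right baseline for this purpose because section 9.1.2 places it before randomisation. The assessment schedule puts reading ii nominally at day 0, one day after open allocation.

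The cost is a sentence in each section and one further model parameter. No new data are needed. It should be settled before the trial statistician is unblinded, which is when section 14.2.2 already requires the analysis plan to be in place.
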